3. RESEARCH DESIGN AND METHODS

Research Design and Methods:

Active duty members and DoD beneficiaries, age 18 years of age or older, meeting the inclusion/exclusion criteria will be offered an opportunity to participate. They will be recruited from the clinics located at Nellis AFB and Scott AFB. All of the below items are research-related unless marked as 'standard of care':

Pre-Eligibility review: Subjects who responded to advertisements or recruitment letters or have given their permission to be contacted will be approached by a study staff member to discuss the subject's interest in the research study and to receive a pre-eligibility screening for study participation. The attached "Pre-Eligibility Review Script" will be used and response will be recorded. If the subject is interested in participating in the study, the study staff member will schedule a screening visit while the subject waits on the phone or in-person, in order to confirm the schedule appointment with the subject. Following the pre-screening procedure, the script will be shredded.

Screening Visit:

- Obtain and document signed Informed Consent document and HIPAA Authorization.
- Review past medical history to verify the inclusion/exclusion criteria including previous encounter, medication list (including analgesic medication currently taking), co-morbidities, demographics, and problems list.

- Record date of birth, age, gender, race, ethnicity, DoD ID, current email address, height (inches), weight (in pounds-not stated weight), obstetrical history, history of relevant pain and interventions.
- Instruct subjects to discontinue any current acupuncture treatment at the onset of entering the study. It is theorized that any acupuncture treatment can have a positive or a negative effect on treatment response regardless of the technique or treatment indication.
- If the subject is an active duty member, we will ask:
 - Have you or are you currently on a fitness restriction for this condition.
 - If so, what are/were the dates of the restriction?

Randomization:

- Subjects will be randomized into one of three research-related treatment groups using block randomization with repeated measures:
 - **Group 1: Scar Deactivation Surface Release Technique protocol:**

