 - Alternating placement of Spring Ten (0.30x40 mm) acupuncture needles to surround scar left in place for a treatment duration of 20 minutes. Needles will be placed at intervals of 1cm to 1.5 cm and will surround the scar with a maximum of 20 needles per treatment.
 - **Group 2: Scar Infiltration with 0.25-1% Lidocaine:**
 - Will consist of calculation of 3 mg/kg dose of 0.5-1% Lidocaine and a dermal followed by subcutaneous injection using 1.5 inch 25 G needle and syringe appropriate for volume based on calculated dose.
 - **Group 3: Physical therapy:**
 - Will be a referral to physical therapy specifying McKenzie protocol treatment for the presenting complaint. The McKenzie protocol is a form of standard of care physical therapy in which the physical therapist tries to find a cause and effect relationship between the positions the patient usually assumes while sitting, standing, or moving, and the location of pain because of those positions or activities. The therapeutic approach requires a patient to move through a series of activities and test movement to gauge the patient's pain response. The approach then uses that information to develop an exercise program designed to centralize or alleviate the pain.

Visit 1 (may be same day as screening visit) (visit window plus or minus 1 week):

Group 1: Scar Deactivation Surface Release Technique protocol (acupuncture):

- Study staff will reconcile medication list (including analgesic medication currently taking).
- Subjects will be weighed (in pounds-not stated weight).
- We will ask what the subjects' expectations are regarding acupunctures effectiveness for chronic, post-surgical pain related to low transverse Cesarean Section.
- The Research Coordinator will record the number of needles placed and the name of the provider performing the acupuncture.
- **Pre-Treatment:**
 - Defense and Veterans Pain Rating Scale (DVPRS)
 - Instruct patients to mark general area of scar on pictures provided on the Patient and Observer Scar Assessment Score (POSAS) Patient Scale.
 - Instruct the PI or AI to complete the POSAS Observer Scale.
- **Post-Treatment:**
 - DVPRS
 - Instruct patients to mark general area of scar on pictures provided the POSAS Patient Scale.
 - Instruct the PI or AI to complete the POSAS Observer Scale.

Group 2: Scar Infiltration with 0.25-1% Lidocaine:

- Study staff will reconcile medication list (including analgesic medication currently taking).

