Describe the method that will be used to create and assign unique study codes to data.	The unique study code will be assigned in sequential order beginning with 001 at each recruiting site. Subjects at Nellis AFB will be named such as NE001 and subjects at Scott AFB will begin with SC001. The code will be placed in a Master Key of identifiable PHI/PII for each subject at each collaborating site					
Describe the method that will be used to create and assign unique study codes to specimens.	 N/A, not collecting specimens					
What is the format of the key?	 Electronic					
Who will have access to the key?	Principal Investigator and/or Designated Research Coordinator at each study site					
Where will the key be stored and how will it be protected?	
Location(s): Each collaborating site will maintain a Master Key of identifiable PHI/PII that will be kept in an electronic database separate from the coded, de-identified research data, which will be encrypted, password protected and the access will be restricted to the PI and/or Designated Research Coordinator. The Master Key will not be stored on any non-government or personal computers or laptops. At the conclusion of the study, the data from each site will be de-identified prior to review and analysis.
 
Confidentiality measures: The coded research data will be kept in a locked cabinet in a locked office and only the research department has the key. The coded research data will be retained until the conclusion of the research study. Once a Final Report has been approved by the IRB, all the paper records will be de-identified and any key linking the subject to their records will be destroyed, based on AFI 33-332, "The Air Force Privacy and Civil Liberties Program" and the National Institute of Standards and Technology Special Publication (NIST SP 800-88) for the approved methods to destroy PII. The anonymized research data will not be utilized for further research activity beyond the protocol stipulations without additional IRB approval.
					

Complete the table.

Source of Research Material per Participant (Procedures)	# Routine Care	# Research Driven	# Total Procedures
DVPRS	0	9	9
POSAS	0	9	9
Acupuncture	0	4	4
Lidocaine	0	4	4

McKenzie Protocol	0	4	4
g. Instrumentation: N/A			

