4. HUMAN SUBJECT PROTECTION

Recruitment and Consent Processes:

All potentially eligible patients will be offered an opportunity to participate. Primary Care Manager (PCM) referrals, with the patient's oral or written authorization, and posted advertisements will be utilized for recruiting subjects to the study. Some patients may be patients of the PI or AI; however, they will have another study staff recruit their patients to prevent any misconception of coercion or undue influence. When a potential subject is identified by the treating PCM, the patient will either be provided a contact number to the Research Staff, the Research Staff will be given the potential subjects contact information by the PCM, or the Research Staff will speak with the patient directly. It is not standard of care to perform this type of acupuncture on pregnant women.

Consent Processes:

Informed Consent and HIPAA authorization will be sought in advance of any screening and study-related procedures from each prospective study subject and appropriately documented in accordance with 32 CFR 219.117. Potential candidates will be notified about the study either through posted advertisements or by their healthcare provider and will be given the opportunity to consent by one of the referred study coordinators. The study coordinator will provide a written copy of the Informed Consent Document (ICD). The subject may decline to consent without prejudice. At the subjects' discretion, they may take the ICD home to discuss further with family members or another physician, prior to making a decision. If they decide they are interested in participating in the study, they can contact the research department. If the subject consents, a copy of the signed ICD and HIPAA Authorization Document will be given to the subject. No vulnerable populations are included in this research study. Subjects who cannot provide Informed Consent will not be allowed to participate. No Legally Authorized Representatives (LAR) will be utilized. Each subject will be asked to place their de-identified research data into the "Nellis Acupuncture Research Data Repository (FWH20140048H) for future research. If the subject does not give their authorization, then the de-identified research data will be destroyed no later than at 3 years after closure of the study.

Recruiting Service Members	Will you be recruiting service members in a group setting?	 Yes	 No

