6. DATA ANALYSIS

Data Analysis:

Outcome Measures:

The primary outcome measures are the Patient and Observer Scar Assessment Scale (POSAS), and the Defense and Veterans Pain Rating Scale (DVPRS).

The Patient and Observer Scar Assessment Scale consists of the total score of two numeric scales measured by the patient and a qualified observer. Each scale assesses the scar by six characteristics on 10-point scales with a 1 corresponding to normal skin and a 10 representing the worst imaginable condition for that characteristic. The Total Score of both scales is calculated by summing scores of the six items resulting in a range of 6 to 60. The POSAS is treated as an interval variable; therefore, parametric methods will be used for this outcome¹⁷.

The DVPRS consists of an 11-point numerical rating scale with 0 indicating no pain and 10 indicating severe pain. It has been confirmed for reliability and validity in measuring both acute and chronic pain, and is currently the standard for pain measurement throughout DoD and VHA health systems. The DVPRS has demonstrated linear scale qualities allowing parametric methods to be used.^{18, 19}.

Outcome Measures:

Primary outcome: Pain reduction and reduction of DVPRS score. The goal for pain reductions will be 50% as a primary outcome.

Secondary outcomes: Reduction of POSAS score, improvement in related and unrelated symptoms as identified by above mentioned questionnaire, and willingness to undergo further treatment.

Sample Size Estimation/Power Analysis:

The study is organized as a mixed effects, randomized complete block design with repeated measures. Subject is a random effect as subjects will have been randomly subjected to C-section from the population of patients obtaining similar care at these Air Force medical treatment facilities, randomly enrolled from this population of patients, and randomly assigned to 3 treatment groups at the time of study enrollment. Fixed effects are treatment group and time of repeated measure as these effects cannot be generalized to other treatments and times.

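### Three visibly different arms are assigned in blocks with no stated safeguard against predicting the next assignment, and the first pain score is taken only after the arm is known

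*Combined protocol and SAP*

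**What the plan says.** **Allocation.** Section 3 (Randomization) states: "Subjects will be randomized into one of three research-related treatment groups using block randomization with repeated measures". Section 6 (Sample Size Estimation/Power Analysis) adds that subjects are "randomly assigned to 3 treatment groups at the time of study enrollment" and describes the design in these terms: "The study is organized as a mixed effects, randomized complete block design with repeated measures". The available text does not give the allocation ratio, the block size, whether sizes vary, whether there is one list or one per site, who generates and holds the list, or how the next assignment is concealed. Section 6 mentions a statistical consultant but gives that role no part in allocation.

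**Who sees what.** Under Consent Processes in Section 4, candidates "will be given the opportunity to consent by one of the referred study coordinators". In the visit schedule of Section 3, "The Research Coordinator will record the number of needles placed and the name of the provider performing the acupuncture", and the same role documents the lidocaine volume in Group 2. The observer part of the scar scale is completed by an investigator: "Instruct the PI or AI to complete the POSAS Observer Scale". No blinding is described.

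**Timing of the first pain score.** The Screening Visit list contains no DVPRS. The first one appears under Visit 1, separately for each group. In all three groups it is listed after a question about what the subject expects from her own assigned treatment.

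**Numbers.** Section 6 plans 30 subjects at each of two sites, 60 in total, and lets one site recruit beyond its share up to the ceiling.

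**The concern.** Blocked allocation has a known weakness when past assignments are visible: as a block fills, the remaining assignments become guessable. Here the arms are unmistakable, and the role that enrols subjects also sees what earlier subjects received. Staff also book the screening visit, so they have some influence on who enters and when. Entry requires abdominal and/or back pain but sets no minimum pain score, so subjects of quite different prognosis can qualify.

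If staff can guess the next arm, they can, even without intending it, bring forward or hold back a patient who seems to suit it. The arms would then differ in ways that were not recorded, and the planned repeated measures analysis of covariance cannot adjust for them. With 60 subjects and equal allocation (an assumption, since no ratio is stated) there are 60 / 3 = 20 per arm, so each steered subject is 1/20 = 5% of an arm.

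The order of the first DVPRS is a separate weakness, and it does not depend on prediction. The primary outcome is reduction in a self-reported score, with a 50% reduction as the goal. A baseline given after the subject knows her arm can be shifted by pleasure or disappointment with it, and every reduction is measured from that baseline.

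**Working it through.** The plan states no predictability figure, so there is nothing to reproduce first. The calculation asks how much a fully informed observer could predict.

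**Inputs from the documents:** three arms, assigned in blocks; 60 subjects, 30 per site.

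**Assumptions, none documented:** 1:1:1 allocation; fixed block size; staff know the size and where each block starts; staff see every earlier assignment on the list, which in practice means one list per site.

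**Blocks of 3.** The chance that the best guess is right is 1/3 at position 1, 1/2 at position 2 and 1 at position 3.
- Mean: (1/3 + 1/2 + 1) / 3 = 11/18 = 61.1%.
- Certain: 1 position in 3, so 60 / 3 = 20 of 60.

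**Blocks of 6 (two of each arm).** The chances at positions 1 to 6 are 1/3, 2/5, 1/2, 8/15, 3/5 and 1.
- Mean: (10 + 12 + 15 + 16 + 18 + 30) / 30 = 101/30; divided by 6, 101/180 = 56.1%.
- Certain: the last position always, and the fifth when the last two are the same arm, which has probability 1/5. So (1 + 1/5) / 6 = 1/5, or 12 of 60.

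**Range over block size, same method by exact enumeration:**

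| Fixed block size | Certain in advance | Best guess right |
|---|---|---|
| 3 | 33.3% | 61.1% |
| 6 | 20.0% | 56.1% |
| 9 | 14.3% | 53.2% |
| 12 | 11.1% | 51.2% |
| 30 | 4.8% | 45.7% |
| Simple randomization | 0% | 33.3% |

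**One list shared by both sites, blocks of 3.** Assume equal, independent accrual and no exchange between sites. The third assignment in a block is certain to the enrolling site only if both earlier subjects were also its own, which has probability 1/2 × 1/2 = 1/4. So 1/3 × 1/4 = 1/12, about 8%, or 5 of 60, rather than 20.

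**Varying sizes that become known.** In a simulation with blocks of 3 or 6 chosen with equal odds, 30 subjects per site and a guesser who knows the two sizes and sees the whole site list, about 8% of assignments are certain but the best guess is still right about 57% of the time. Varying the sizes removes most of the certainty. It does not stop good guessing if the sizes are disclosed.

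**Position of the first DVPRS.** The procedures table in Section 3 lists 9 DVPRS per participant. Groups 1 and 2 have two at each of Visits 1 to 4 and one at Visit 5: 4 × 2 + 1 = 9. None is left for screening. The first score is therefore inside the group-specific Visit 1, after assignment.

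**The case against.** A reader might infer that staff will be able to deduce the next arm, with one in three known for certain. The documents do not support that. They give no block size. The description "The study is organized as a mixed effects, randomized complete block design with repeated measures" sits in the power section and introduces a mixed model with random and fixed effects. It does not describe the allocation list. Blocks of three are its classical reading for three treatments, but larger balanced blocks fit the Randomization wording equally well. Nor is it stated that staff know the block boundaries, or that each site has its own list.

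A reader might also take the subject codes as the route to prediction: "The unique study code will be assigned in sequential order beginning with 001 at each recruiting site". That sentence belongs to the plan for protecting identities, where access to the key is limited to the "Principal Investigator and/or Designated Research Coordinator at each study site". Nothing ties the codes to the allocation list, and staff can count their own enrolments without them.

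Some safeguards exist. Consent and eligibility review come before randomization, all potentially eligible patients are to be offered the study, and investigators have other staff recruit their own patients. These limit steering but do not conceal the list. The attachments, including the Procedure Instructions, were not available and may say more. No effect on the DVPRS can be estimated from the documents.

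What stands is narrower. Blocks, visible arms and overlapping roles are documented, and the available text contains no countermeasure. The late first DVPRS follows from the schedule itself and needs none of the assumptions about blocks.

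**Conclusion.** The point holds in two parts.

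First, the available text does not exclude prediction of assignments in a trial where the enrolling role can see the treatments given. The possible size runs from 33.3% of assignments certain (blocks of 3) to 4.8% (blocks of 30), with the best guess right 61.1% to 45.7% of the time against 33.3% by chance. All of these are upper bounds that rest on fixed, known blocks and full sight of the list. Under a shared list with blocks of 3, the certain share falls to about 8%. That prediction would occur, or that anyone would act on it, is not shown.

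Second, baseline pain is recorded after the arm is known. That is the order as written, and it affects the starting value of a self-reported primary outcome.

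Both should be changed because the remedy is cheap and the damage could not be repaired in the analysis. Confidence in the size of the first part is moderate at best, because it depends on a block size that the plan does not give.

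**What to change.** Amend the Randomization part of Section 3 to say, in substance:

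- The statistical consultant mentioned by role in Section 6 prepares the allocation list and holds it away from the sites.
- The list uses permuted blocks whose sizes vary at random. The sizes are recorded in a document that the sites do not see.
- Each assignment is released only after consent, confirmed eligibility and the first DVPRS have been recorded.

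The block sizes must not be printed in the protocol, because site staff work from it. As shown above, once the sizes are known the best guess is right about as often as with a fixed block of 6.

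**Cost.** One protocol passage, a new list, and a simple release step, for example sealed opaque envelopes prepared by the statistician. Numbered envelopes kept at each site imply one sequence per site, so non-disclosure of the sizes then matters most. Varying the blocks allows a slightly larger imbalance in arm sizes. The existing pre-treatment DVPRS of Visit 1 (the single Visit 1 score in Group 3) moves ahead of the release, so the planned number of DVPRS assessments does not change. Where Visit 1 is not on the same day as screening, releasing the assignment at the start of Visit 1 keeps that score close to treatment.

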- Subjects will be weighed (in pounds-not stated weight).
- We will ask what the subjects' expectations are regarding lidocaine's effectiveness for chronic, post-surgical pain related to low transverse Cesarean Section.
- The Research Coordinator will document the total volume of 0.5-1% Lidocaine injection.
- **Pre-Treatment:**
 - DVPRS

- Instruct patients to mark general area of scar on pictures provided on the POSAS Patient Scale.
- Instruct the PI or AI to complete the POSAS Observer Scale.
- Post-Treatment:
 - DVPRS
 - Instruct patients to mark general area of scar on pictures provided the POSAS Patient Scale.
 - Instruct the PI or AI to complete the POSAS Observer Scale.

Group 3: Physical Therapy:

- Study staff will reconcile medication list (including analgesic medication currently taking).
- Subjects will be weighed (in pounds-not stated weight).
- We will ask what the subjects' expectations are regarding physical therapy's effectiveness for chronic, post-surgical pain related to low transverse Cesarean Section.
- Subjects will be given a study diary and asked to track the dates and duration of their physical therapy treatments.
- DVPRS
- Instruct patients to mark general area of scar on pictures provided on the POSAS Patient Scale.
- Instruct the PI or AI to complete the POSAS Observer Scale.

Visit 2 (4 weeks after visit 1 (visit window plus or minus 1 week)):

Group 1: Scar Deactivation Surface Release Technique protocol (acupuncture):

- Study staff will reconcile medication list (including analgesic medication currently taking).
- Subjects will be weighed (in pounds-not stated weight).
- The Research Coordinator will record the number of needles placed and the name of the provider performing the acupuncture.
- Pre-Treatment:
 - DVPRS
 - Instruct patients to mark general area of scar on pictures provided on the POSAS Patient Scale.
 - Instruct the PI or AI to complete the POSAS Observer Scale.
- Post-Treatment:
 - DVPRS
 - Instruct patients to mark general area of scar on pictures provided the POSAS Patient Scale.
 - Instruct the PI or AI to complete the POSAS Observer Scale.

Group 2: Scar Infiltration with 0.25-1% Lidocaine:

- Study staff will reconcile medication list (including analgesic medication currently taking).
- Subjects will be weighed (in pounds-not stated weight).
- The Research Coordinator will document the total volume of 0.5-1% Lidocaine injection.
- Pre-Treatment:
 - DVPRS

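### No DVPRS or POSAS score is taken before allocation, so the DVPRS-based reduction rests on a baseline not protected from knowledge of the assigned arm

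*Combined protocol and SAP*

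**What the plan says.** Section 3 sets out the Screening Visit, then Randomization, then Visit 1.

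- **Screening Visit.** It covers consent, medication and medical history, demographics, height, weight and fitness restrictions. The nearest item to a pain measure is "obstetrical history, history of relevant pain and interventions", which is not a scored scale.
- **Randomization.** "Subjects will be randomized into one of three research-related treatment groups using block randomization with repeated measures". Section 6 gives the timing: subjects are "randomly assigned to 3 treatment groups at the time of study enrollment".
- **Visit 1.** It can fall on the screening day or later. DVPRS and both POSAS scales appear here for the first time, under a separate heading for each group. They are marked as pre-treatment in Groups 1 and 2 and taken once in Group 3. For the observer part the instruction is "Instruct the PI or AI to complete the POSAS Observer Scale".
- **Expectations.** Each group is asked at Visit 1 about its own treatment only: "We will ask what the subjects' expectations are regarding acupunctures effectiveness" in Group 1, "We will ask what the subjects' expectations are regarding lidocaine's effectiveness" in Group 2 and "We will ask what the subjects' expectations are regarding physical therapy's effectiveness" in Group 3.

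Section 6 makes reduction of DVPRS the primary outcome, with a 50% goal for pain reduction, and plans a mixed-effects rANCOVA. It names neither the baseline nor the covariate. Neither section describes blinding of subjects or of the observer.

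**The concern.** Pain and scar ratings are subjective. A subject who has just learned that she will be needled, injected or referred to physical therapy may rate her pain differently because of it, and so may the investigator who scores her scar. If that happens unequally across arms, the reference value itself differs by arm, and the difference can appear as a treatment effect or hide one. Adjusting for a score taken after allocation removes only part of such a shift, because the covariate has itself been exposed to allocation. In addition, a subject lost between allocation and Visit 1 has no score at all and cannot enter any analysis of change.

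**Working it through.** **1. Is a screening score planned but missing from the list?** The procedures table in Section 3 gives 9 DVPRS and 9 POSAS assessments per participant. In Groups 1 and 2 the schedule gives Visits 1-4 × (pre + post) + Visit 5 = 4 × 2 + 1 = 9. This reproduces the table and leaves 9 − 9 = 0 for screening. Group 3, scored once per visit, has 5. The absence is therefore the design, not a dropped line.

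**2. Do the parties know the arm at the first score?** The documents do not use the word open. Three things point that way: the expectation question names the subject's own treatment, the three treatments are visibly different, and no blinding is described.

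**3. What could a shift do to the 50% goal?** Take the Section 6 DVPRS mean of 4.4 and a true fall to 2.2 (50%). If one arm's baseline alone is raised by b (assumed):

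- b = 0.5: 1 − 2.2/4.9 = 55.1%
- b = 1.0: 1 − 2.2/5.4 = 59.3%

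With no true change, the apparent reductions are 0.5/4.9 = 10.2% and 1.0/5.4 = 18.5%.

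**4. What could it do to the type I error?** From Section 6: SD 2.4, and 45 subjects required, so 15 per arm if allocation is equal (the ratio is not stated). The 48 planned completers would give 16. Assumed: baseline to follow-up correlation ρ = 0.5, no true difference between two arms, and a shift in one arm's baseline only.

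- Change score: bias b; SE = 2.4 × √(2(1 − ρ)) × √(2/15) = 2.4 × 0.365 = 0.876.
- Baseline-adjusted: bias ρb; SE = 2.4 × √(1 − ρ²) × √(2/15) = 2.078 × 0.365 = 0.759.
- Error, with z = bias/SE: 1 − Φ(1.96 − z) + Φ(−1.96 − z).

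| Shift b | z, change | Error | z, adjusted | Error |
|---|---|---|---|---|
| 0.5 | 0.571 | 8.8% | 0.329 | 6.3% |
| 1.0 | 1.141 | 20.7% | 0.659 | 10.1% |

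A noncentral t calculation with 15-16 per arm gives 8.5-8.8% and 19.7-20.7% for change scores, and about 6% and 10% adjusted. Over ρ = 0.3 to 0.7 with 15 per arm, the normal approximation gives:

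- b = 0.5: 7.7-11.4% (change), 5.4-8.7% (adjusted)
- b = 1.0: 16.1-31.3% (change), 6.5-20.1% (adjusted)

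**5. What if the shift persists?** Let a share p of the shift carry into the follow-up rating. The change-score bias becomes (1 − p)b and the adjusted bias (ρ − p)b. With b = 1.0 and ρ = 0.5:

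- p = 0.5: biases 0.5 and 0, so errors of 8.8% and 5.0%.
- p = 1: biases 0 and −0.5, so errors of 5.0% and 10.1%, the latter in the opposite direction.

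**The case against.** Several stronger readings are tempting, and the documents do not support them.

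- **That the baseline is biased.** A reader might infer this from the sequence. The documents show only that the baseline is unprotected. In Groups 1 and 2 the score still precedes treatment, and nothing shows that ratings move or which way.
- **That subjects state their expectations before they score.** This rests on bullet order, which is not chronological: the same lists put the needle count and the lidocaine volume ahead of the pre-treatment scores. The order is simply unstated.
- **That every pain-reduction result depends on the Visit 1 score.** Visit 5 also records a self-reported percentage reduction since the start of the study, Visits 2-4 have their own pre/post pairs in Groups 1 and 2, and Section 6 does not tie the 50% goal to DVPRS.
- **That the expectation item fails as a covariate.** No section plans that use. It pairs naturally with the Visit 5 question on whether expectations were met.
- **That the error rate is 9-21%.** Those figures are for a two-arm change-score test. The plan is an rANCOVA followed by contrasts, with Holm correction where multiple comparisons are made.

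The most substantial objection concerns persistence. If the whole shift carried into later ratings, the contaminated baseline would cancel it in a change score. A clean baseline would then leave a bias of 1.0 (b = 1.0, ρ = 0.5): z = 1.0/0.876 = 1.141 and 1.0/0.759 = 1.318, or about 21% and 26% error. The arithmetic is right, but that bias belongs to the unblinded follow-up ratings, which are a separate problem. A contaminated baseline would offset it only by chance.

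A last objection also stands in part. Subjects stop current acupuncture on entry, so when Visit 1 is later, change from a screening score spans that withdrawal. Randomization balances this between arms but not within an arm, and the Section 2 hypotheses are about reduction within each treatment.

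**Conclusion.** The point holds as a matter of design: no DVPRS or POSAS score precedes allocation, and the first scores are taken when subject and rater can be expected to know the arm. The DVPRS-based reduction, and the 50% goal if computed from DVPRS, therefore lack a protected reference, and a subject lost before Visit 1 has none.

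The sequence is well established; the effect is a risk of unknown size and direction. The figures of about 6-10% (adjusted) and 9-21% (change score) are illustrations. They depend on an assumed shift confined to one arm's baseline, an assumed correlation and equal allocation. The adjusted figure also assumes that baseline is the rANCOVA covariate, which Section 6 does not say. Persistence into follow-up would lower the change-score figure; it would first lower the adjusted bias and then reverse it. The remedy is cheap, so the change should be made, but this does not show that the trial's results would be wrong.

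**What to change.** 1. Add DVPRS, the POSAS Patient Scale and the POSAS Observer Scale to the Screening Visit after consent, and state that randomization follows their completion.
2. In Section 6, name these scores as the baseline for the between-arm rANCOVA and for the 50% goal where it is computed from DVPRS.
3. Ask the expectation question either before allocation or no earlier than the scores, and state the order. Asking every subject about all three treatments is optional.
4. When Visit 1 is on a later day, keep its pre-treatment score as the anchor for same-day pre/post change. Report within-arm change from it as well, because of the acupuncture stop on entry.

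**Cost.** A short amendment, with no extra visit and no change in sample size. When both visits fall on one day it is mainly a change of order. Otherwise there is one extra questionnaire set, making 9 + 1 = 10 assessments in Groups 1 and 2 and 5 + 1 = 6 in Group 3, and the procedures table needs updating. The change does not cure unblinded follow-up ratings.
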